1. **Definite** (either by angiographic or pathologic confirmation):
 - a. Angiographic confirmation of stent thrombosis is considered to have occurred if:
 - i. Thrombolysis In Myocardial Infarction (TIMI) flow is:
 1. TIMI flow grade 0 with occlusion originating in the stent or in the segment 5mm proximal or distal to the stent region in the presence of a thrombus
 2. TIMI flow grade 1, 2, or 3 originating in the stent or in the segment 5mm proximal or distal to the stent region in the presence of a thrombus
 - ii. AND at least one of the following criteria has been fulfilled within a 48 hour time window:
 1. New onset of ischemic symptoms at rest (typical chest pain with duration >20 minutes)
 2. New ischemic ECG changes suggestive of acute ischemia
 3. Typical rise and fall in cardiac biomarkers (refer to definition non-procedural related MI).
 - b. Pathologic confirmation of stent thrombosis:

Evidence of recent thrombus within the stent determined at autopsy or via examination of tissue retrieved following thrombectomy.

*Note: The incidental angiographic documentation of stent occlusion in the absence of clinical signs or symptoms is **not** considered a confirmed stent thrombosis (silent occlusion).*

2. Probable:

Clinical definition of probable stent thrombosis is considered to have occurred after intracoronary stenting in the following cases:

- a. Any unexplained death within the first 30 days.

RESOLUTE Onyx 2.0 mm Clinical Study**CONFIDENTIAL - May not be reproduced without written permission from Medtronic**

- b. Irrespective of the time after the index procedure any myocardial infarction (MI), which is related to documented acute ischemia in the territory of the implanted stent without angiographic confirmation of stent thrombosis and in the absence of any other obvious cause.

3. Possible:

Clinical definition of possible stent thrombosis is considered to have occurred with any unexplained death from 30 days following intracoronary stenting until end of trial follow-up.

STROKE

Defined as sudden onset of vertigo, numbness, dysphasia, weakness, visual field defects, dysarthria or other focal neurological deficits due to vascular lesions of the brain such as hemorrhage, embolism, thrombosis, or rupturing aneurysm, that persists more than 24 hours.

STUDY DEVIATION

A study deviation is defined as an event where the Investigator or site personnel did not conduct the trial according to the investigational plan, applicable laws or regulations, or the Investigator Agreement.

STUDY STENT

A study stent is defined as the Resolute Onyx 2.0 mm stent.

TARGET LESION

Any lesion treated or attempted to be treated during the study procedure. The target lesion is the treated segment starting 5 mm proximal to the stent and ending 5 mm distal to the stent.

TARGET LESION FAILURE (TLF)

Defined as cardiac death, target vessel myocardial infarction (Q wave and non-Q wave), or clinically-driven target lesion revascularization (TLR) by percutaneous or surgical methods

TARGET LESION REVASCULARIZATION (TLR)

Repeat PCI or CABG to the target lesion. See also clinically-driven target lesion revascularization.

TARGET VESSEL

The arterial segment and any branches and/or parent vessel that possess the target lesion. For this study, the target vessel can only be the left main (protected), LAD, Cx, RCA. Side branches less than 2.0 mm in diameter will not be considered 'significant' and therefore the disease in these vessels will not be considered significant.

RESOLUTE Onyx 2.0 mm Clinical Study**CONFIDENTIAL - May not be reproduced without written permission from Medtronic**

TARGET VESSEL FAILURE (TVF)

The composite endpoint comprised of cardiac death, target vessel myocardial infarction, or clinically-driven target vessel revascularization by percutaneous or surgical methods.

Target vessel failure will be reported when ANY of the following events occur:

- Recurrent MI occurs in territory not clearly attributed to a vessel other than the target vessel.
- Cardiac death not clearly due to a non-target vessel endpoint.
- Target vessel revascularization is determined.

TARGET VESSEL MYOCARDIAL INFARCTION (TVMI)

Target-vessel MI is defined as a MI that occurs in a territory that cannot be clearly attributed to a vessel other than the target vessel.

TARGET VESSEL REVASCULARIZATION (TVR)

Repeat PCI or CABG of the target vessel. See also clinically-driven target vessel revascularization.

THROMBOLYSIS IN MYOCARDIAL INFARCTION (TIMI) CLASSIFICATION¹⁵

TIMI 0	No perfusion.
TIMI 1	Penetration with minimal perfusion. Contrast fails to opacify the entire bed distal to the stenosis for the duration of the cine run.
TIMI 2	Partial perfusion. Contrast opacifies the entire coronary bed distal to the stenosis. However, the rate of entry and/or clearance is slower in the coronary bed distal to the obstruction than in comparable areas not perfused by the dilated vessel.
TIMI 3	Complete perfusion. Filling and clearance of contrast equally rapid in the coronary bed distal to stenosis as in other coronary beds.

RESOLUTE Onyx 2.0 mm Clinical Study**CONFIDENTIAL - May not be reproduced without written permission from Medtronic****THROMBUS (INTRACORONARY)¹⁶**

Non-occlusive thrombus: Intracoronary thrombus is defined as a (spheric, ovoid or irregular) non-calcified filling defect or lucency surrounded by contrast material (on three sides or within a coronary stenosis) seen in multiple projections, or persistence of contrast material within the lumen, or a visible embolization of intraluminal material downstream.

Occlusive thrombus: TIMI 0 or TIMI 1 intra-stent or proximal to a stent up to the most adjacent proximal side branch or main branch (if originating from the side branch).

TOTAL OCCLUSION

A total occlusion is defined as a lesion with no flow (TIMI 0). Total occlusions are usually classified as persisting less than or more than 3 months (chronic total occlusion).

TRANSIENT ISCHEMIC ATTACK (TIA)

A TIA is defined as a focal neurological abnormality of sudden onset and brief duration (lasting less than 24 hours) that reflect dysfunction in the distribution of the effected artery. TIAs include transient monocular blindness (e.g., amaurosis fugax defined as a transient episode of monocular blindness, or partial blindness, lasting ten minutes or less) and transient hemispheric attacks.

UNANTICIPATED ADVERSE DEVICE EFFECT (UADE)

An UADE is defined as any serious adverse effect on health or safety or any life-threatening problem or death caused by, or associated with, a device, if that effect, problem, or death was not previously identified in nature, severity, or degree of incidence in the investigational plan or application (including a supplementary plan or application), or any other unanticipated serious problem associated with a device that relates to the rights, safety, or welfare of subjects.

UNSTABLE ANGINA

Per the ACC/AHA 2002 Guideline Update for the Management of Subjects with Unstable Angina and Non-ST-Segment Elevation Myocardial Infarction there are three (3) principal presentations of unstable angina (UA)¹⁷:

1. Rest Angina. Angina occurring at rest and prolonged, usually >20 minutes.
2. New-onset Angina. New-onset angina of at least CCS Class III Severity.
3. Increasing Angina. Previously diagnosed angina that has become distinctly more frequent, longer in duration, or lower in threshold (i.e., increased by greater than or equal to 1 CCS class to at least CCS Class III severity).

RESOLUTE Onyx 2.0 mm Clinical Study**CONFIDENTIAL - May not be reproduced without written permission from Medtronic**

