5.5.3 Cardiac Biomarkers

Creatine Kinase (CK) enzyme and troponin will be measured post-procedure following removal of the last catheter as follows:

- 1st draw: >3 hours, <12 hours post procedure
- 2nd draw: >4 hours after 1st draw, <24 hours post procedure

Cardiac enzymes/biomarkers will be collected if they are related to a trial primary or secondary endpoint, including but not limited to death, (suspected) MI or stent thrombosis. These may include creatine kinase (CK) enzyme, creatine kinase myocardial-band (CK-MB) isoenzyme and troponin.

If it is not standard hospital practice to measure CK values, CK-MB values are sufficient. All subjects should have Troponin values.

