CONFIDENTIAL - May not be reproduced without written permission from Medtronic

LATE LUMEN/LUMINAL LOSS

Defined as the difference between the post-procedure minimal lumen diameter (MLD) and the follow-up angiography MLD.

LESION CLASS (American College of Cardiology/American Heart Association Class)¹⁴

- Type A Lesions:** Minimally complex, discrete (length < 10 mm), concentric, readily accessible, non-angulated segment (< 45°), smooth contour, little or no calcification, less than totally occlusive, not ostial in location, no major side branch involvement, and an absence of thrombus.
- Type B Lesions:** Moderately complex, tubular (length 10 to 20 mm), eccentric, moderate tortuosity of proximal segment, moderately angulated segment (> 45°, < 90°), irregular contour, moderate or heavy calcification, total occlusions < 3 months old, ostial in location, bifurcation lesions requiring double guidewires, and some thrombus present.
- Type B1:* One adverse characteristic.
- Type B2:* Two or more adverse characteristics.
- Type C Lesions:** Severely complex, diffuse (length > 20 mm), excessive tortuosity of proximal segment, extremely angulated segments > 90°, total occlusions > 3 months old and/or bridging collaterals, inability to protect major side branches, and degenerated vein grafts with friable lesions.

LESION SUCCESS

Attainment of < 50 % residual stenosis of the target lesion using any percutaneous method.

MAJOR ADVERSE CARDIAC EVENTS (MACE)

Defined as death, myocardial infarction (Q wave and non-Q wave), emergent coronary bypass surgery, or clinically-driven repeat target lesion revascularization by percutaneous or surgical methods.

MINIMAL LUMINAL DIAMETER (MLD)

The average of two orthogonal views (when possible) of the narrowest point within the area of assessment – in lesion, in stent or in segment. MLD is visually estimated during angiography by the Investigator; it is measured during QCA by the Angiographic Core Laboratory.

MYOCARDIAL INFARCTION (MI)

All myocardial infarction data will be reported per Medtronic historical protocol definitions.

RESOLUTE Onyx 2.0 mm Clinical Study
CONFIDENTIAL - May not be reproduced without written permission from Medtronic

Q wave MI (QWMI): will require one of the following criteria:

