Chest pain or other acute symptoms consistent with myocardial ischemia and new pathological Q waves in two or more contiguous ECG leads as determined by an ECG core laboratory or independent review of the CEC, in the absence of timely cardiac enzyme data.

New pathologic Q waves in two or more contiguous ECG leads as determined by an ECG core laboratory or independent review of the CEC and elevation of cardiac enzymes. In the absence of ECG data the CEC may adjudicate Q wave MI based on the clinical scenario and appropriate cardiac enzyme data.

Medtronic Historical Definition of Non-Q Wave MI (NQWMI): elevated CK $\geq 2X$ the laboratory upper limit of normal with the presence of an elevated CK-MB (any amount above the laboratory upper limit of normal) in the absence of new pathological Q waves.

Extended Historical Definitions:

I. PCI (PERCUTANEOUS CORONARY INTERVENTION)

Ia. Baseline Biomarkers of Myocardial Damage (CK and CKMB and Trop $< 1*URL$) and not acute MI in progress.

PERIPROCEDURAL <48 HOURS POST PCI

A. New pathologic q waves in ≥ 2 contiguous ECG leads AND:
 
 ▪ any CKMB $> 1*URL$ or ▪ in the absence of CKMB: Troponin $> 1*URL$ or ▪ in the absence of CKMB and Troponin: CK $> 1*URL$ or ▪ in the absence of CKMB and Troponin and CK: CEC decision upon clinical scenario 
B. Appropriate cardiac enzyme data (respecting top-down hierarchy, b1 to b3):
 
b1. CK $\geq 2* URL$ Confirmed by :
 
 ▪ CKMB $> 1*URL$ or ▪ in the absence of CKMB:, Troponin $> 1*URL$ or ▪ in the absence of CKMB and Troponin: CEC decision upon clinical scenario 
OR
 
b2. In the absence of CK: CKMB $> 3*URL$
 
OR
 
b3. In the absence of CK and CKMB: Troponin $> 3*URL$

Note: URL = upper reference limit, defined as 99th percentile of normal reference range

RESOLUTE Onyx 2.0 mm Clinical Study**CONFIDENTIAL - May not be reproduced without written permission from Medtronic****Ib. If Baseline Biomarkers of Myocardial Damage: CK and/or CKMB > 1*URL *or* acute MI in progress****MYOCARDIAL INFARCTION, RE-INFARCTION (EXTENSION) <48 HOURS POST PCI**

A. If CK (or CKMB) from index MI has not yet reached its maximum level:

- Recurrent thoracic chest pain or ischemia equivalent >20 minutes (or new ECG changes consistent with MI)

AND

▪ Appropriate cardiac enzyme data:

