6.3. Analysis of Secondary Endpoints

Descriptive statistics for the secondary endpoints will be provided. Categorical variables will be reported using counts and percentages, and continuous variables will be reported by giving the number of known values, the mean, standard deviation, minimum and maximum values. The time-sensitive nature of any response variable may be displayed by using a Kaplan-Meier plot. For the myocardial infarctions (MI) component of the endpoints, the extended historical MI definitions will be used.

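### Does the SAP leave open which MI definition decides target-vessel MI in the primary TLF?

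*Protocol*

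**What the plan says.** Protocol Appendix 2, under Myocardial Infarction, opens with "All myocardial infarction data will be reported per Medtronic historical protocol definitions". Two sets of rules for a non-Q-wave MI follow under that heading.

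- **Plain rule:** CK at least 2x the laboratory upper limit of normal, "with the presence of an elevated CK-MB (any amount above the laboratory upper limit of normal"), and no new pathological Q waves. It has no alternative if a marker was not measured.
- **Extended set, row Ia (first 48 hours after PCI, normal baseline):** CK at least 2x the upper reference limit (URL), confirmed by CK-MB above the URL. If CK-MB is missing, troponin above the URL confirms. If CK is missing, CK-MB above 3x the URL suffices. If both are missing, troponin above 3x the URL suffices.

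On blood draws, Protocol 5.5.3 says "Creatine Kinase (CK) enzyme and troponin will be measured post-procedure following removal of the last catheter as follows", and adds "If it is not standard hospital practice to measure CK values, CK-MB values are sufficient". For events related to an endpoint, including a suspected MI, further markers are collected: "These may include creatine kinase (CK) enzyme, creatine kinase myocardial-band (CK-MB) isoenzyme and troponin".

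The only sentence that chooses between the two sets is in SAP 6.3, on secondary endpoints: "For the myocardial infarctions (MI) component of the endpoints, the extended historical MI definitions will be used". SAP 3.2.1, SAP 6.2 and Protocol 7.4, which deal with the primary endpoint, name no MI definition.

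**The concern.** The primary result turns on a count of TLF events, and TVMI is one of its components. The protocol's minimum draws never yield CK and CK-MB together, yet the plain rule needs both. A subject with CK 2.5x and raised troponin, or with CK-MB 4x and no CK, is an MI under the extended set and not under the plain rule.

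If the choice were open, it could decide the trial. One event separates success from failure at the boundary, and on these draws the plain rule can only lower the count, which favours meeting the 19% goal. The study is open-label, so a definition chosen late would be chosen with the data in view. The missing-data analyses in SAP 6.2 would not show the difference: they cover only subjects who drop out before day 330, whereas a followed subject whose MI is not counted stays in the denominator as TLF-free (SAP 6.1).

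**Working it through.** **1. The plan's own figure.** Inputs from SAP 3.3: 100 subjects, 10% loss (100 x 0.9 = 90 evaluable), goal 19%, assumed rate 9.4%, one-sided 0.05. By the normal approximation:

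(0.19 - 0.094 - 1.645 x sqrt(0.19 x 0.81 / 90)) / sqrt(0.094 x 0.906 / 90) = 0.0280 / 0.0308 = 0.91, so power is 0.8185.

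This reproduces the stated figure of more than 80%. The exact limit planned in SAP 6.2 gives 77.6% with 90 evaluable and 85.5% with 100; that difference is a separate matter.

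**2. Where the boundary lies.** Exact one-sided 95% upper limits:

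| Evaluable | Largest passing count | Upper limit | Next count | Upper limit |
|---|---|---|---|---|
| 90 | 10 | 18.12% | 11 | 19.42% |
| 100 | 12 | 18.72% | 13 | 19.87% |

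**3. Where the rules differ.** Both rules were applied to marker patterns with a normal baseline, within 48 hours, without new Q waves, and treating the laboratory limit and the URL as the same cut-off.

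| Markers available | Example | Plain rule | Extended set |
|---|---|---|---|
| CK + troponin | CK 2.5x, troponin 2x | cannot be met (no CK-MB) | MI, troponin fallback |
| CK-MB + troponin | CK-MB 4x | cannot be met (no CK) | MI, CK-MB fallback |
| CK + CK-MB + troponin | 12 patterns | same as extended | same as plain |

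With full markers there is no disagreement. Every disagreement comes from a fallback such as "in the absence of CKMB: Troponin", used where the plain rule lacks a marker it needs. There the plain rule is not assessable; it has not observed a negative.

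**4. What would be at stake if the choice were open.** Let h be the share of subjects whose only TLF event counts under the extended set but not under the plain rule. The documents give no value, so h is an assumption; it is zero if every site measures both CK and CK-MB. When the plain count cannot exceed the extended count, P(different verdict) = P(pass at 9.4% - h) - P(pass at 9.4%).

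| h (points) | 90 evaluable | 100 evaluable |
|---|---|---|
| 0.5 | 0.8243 - 0.7764 = 4.8% | 0.8932 - 0.8555 = 3.8% |
| 1 | 0.8665 - 0.7764 = 9.0% | 0.9241 - 0.8555 = 6.9% |
| 2 | 0.9316 - 0.7764 = 15.5% | 0.9668 - 0.8555 = 11.1% |

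**5. Is the choice open?** Four places bear on it.

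- SAP 6.3 speaks of the MI component of the endpoints, without limiting it to secondary ones.
- Even read strictly within its heading, it settles 12-month TLF: SAP 3.2.2 lists both TVMI and TLF, assessed at 12 months among other times, as secondary endpoints. A different rule for the primary would give the same variable at the same time two values, and nothing asks for that.
- Where Appendix 2 wants two parallel counts it says so: acute success is to be reported under both the historical and the current definitions. For MI there is one family of historical definitions, with the extended set inside it.
- Protocol 10.3 has the Clinical Events Committee set its minimum data and its classification algorithm at study onset. Its members do not take part in the study.

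**The case for a change.** The strongest reply is that a pass/fail endpoint should not rest on inference. The choice sits under the wrong heading for the primary, the Appendix 2 lead sentence does not name the extended set, and the only rule labelled as the historical definition of a non-Q-wave MI is the plain one. The committee's algorithm is promised, but neither document says which definition it uses. Extra CK-MB at a suspected MI is possible, not guaranteed, and a periprocedural MI shown by enzymes alone may raise no suspicion.

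The placement point stands: SAP 6.2 is silent and a cross-reference would have been tidier. It does not follow that two defensible counts exist. The plain rule often cannot be evaluated on the required draws, so an analyst with SAP 6.3 in hand has no reason to prefer it.

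Three smaller points also remain, and none alters the conclusion.

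- The plain rule uses the laboratory limit and the extended set the 99th percentile, so cut-offs may differ slightly even with full markers.
- With raised baseline CK or CK-MB, the extended set can ask for a 50% rise that the plain rule does not, so the difference could run the other way. The formula in step 4 does not cover that. Those rows are worded for an index MI, and Protocol 4.4.3 excludes acute MI within 72 hours.
- The row beginning "Ia. Baseline Biomarkers of Myocardial Damage (CK and CKMB and Trop" requires all three markers to be normal at baseline, and the next row names only CK, CK-MB or an acute MI. Raised baseline troponin alone therefore falls between them. Exclusion 5b removes such subjects if they also have ischemic symptoms or the listed ECG or imaging changes. Any others are few, possibly none, and fall to the committee's algorithm.

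**Conclusion.** The concern does not call for a change. It is a gap that analysts fill sensibly: followed as written, the plan applies the extended historical definitions to 12-month TLF, and those are the definitions that work on the required CK (or CK-MB) and troponin draws. The primary result is sound on that reading.

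The sensitivity is real in principle, since 10 of 90 passes and 11 of 90 fails, but that holds for any exact binomial cut-off. The 4.8% to 15.5% range for 90 evaluable subjects (3.8% to 11.1% for 100) would apply only if the plain rule were used in place of the one SAP 6.3 names, and only for an assumed h of 0.5 to 2 points. The documents neither support that range nor exclude zero. They also do not show that the definition would be settled after the data exist. A supportive count under the plain rule would add little, because that rule cannot be assessed on the minimum draws and would undercount.

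This rests on reading SAP 6.3 as covering 12-month TLF, which its wording and the list in SAP 3.2.2 support, and on the committee's algorithm agreeing with it. That algorithm is not in the documents reviewed.

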Appendix 3: Investigator's Brochure/Report of Prior Investigations

NOTE: Refer to the most current version of the Investigator's Brochure/Report of Prior Investigations sent under separate cover.

RESOLUTE Onyx 2.0 mm Clinical Study**CONFIDENTIAL - May not be reproduced without written permission from Medtronic**

Appendix 4: Sample Subject Informed Consent Form

NOTE: Refer to the most current version of the Sample Subject Informed Consent Form and Authorization to Use and Disclose Health Information sent under separate cover.

RESOLUTE Onyx 2.0 mm Clinical Study
CONFIDENTIAL - May not be reproduced without written permission from Medtronic

Appendix 5: Sample Case Report Forms

NOTE: Refer to the most current version of the case report forms sent under separate cover.

RESOLUTE Onyx 2.0 mm Clinical Study**CONFIDENTIAL - May not be reproduced without written permission from Medtronic**

Appendix 6: Study Device Instructions For Use

NOTE: Refer to the most current version of the instructions for use sent under separate cover or packaged with the device.

RESOLUTE Onyx 2.0 mm Clinical Study**CONFIDENTIAL - May not be reproduced without written permission from Medtronic**

Appendix 7: Angiographic Core Laboratory Procedures

NOTE: Refer to the most current version of the Angiographic Core Laboratory Procedures sent under separate cover.

RESOLUTE Onyx 2.0 mm Clinical Study**CONFIDENTIAL - May not be reproduced without written permission from Medtronic**

Appendix 8: Japan specific

NOTE: Applicable to Japan sites only - sent under separate cover.

RESOLUTE Onyx 2.0 mm Clinical Study
CONFIDENTIAL - May not be reproduced without written permission from Medtronic

Appendix 9: Center for Medicare and Medicaid Services (CMS) IDE Study Criteria – Applicable to US sites only

Medicare Beneficiaries

The results of this study are expected to be applicable to a significant number of Medicare beneficiaries based on incidence of cardiovascular disease, number of percutaneous coronary interventions, and number of patients with relevant luminal reference diameters of the culprit coronary artery in this population.

A 2010 report published by the Centers for Disease Control (CDC) found that coronary heart disease was the most common subtype of heart disease hospitalization, representing 42.0 % of all Medicare heart disease hospitalizations.⁽¹⁾

Analyses of percutaneous coronary interventions among Medicare beneficiaries showed the following number of PCI episodes (both admission and non-admission) from 2008 to 2012⁽²⁾:

- 2008: 423,789 PCI episodes
- 2009: 426,518 PCI episodes
- 2010: 434,134 PCI episodes
- 2011: 417,963 PCI episodes
- 2012: 401,929 PCI episodes

These numbers are expected to increase over the next 15 years based on the baby boom generation reaching Medicare age, as well as the current incidence of cardiac revascularizations performed on Medicare beneficiaries.⁽²⁾

With regard to the specific populations that may benefit from the Resolute Onyx 2.0 mm, diameter device, the Journal of the American College of Cardiology published a study showing that among a study of 2,306 patients, 35% (n=813 patients) with a mean age of 65 were found to have a luminal reference diameters of less than or equal to 2.5 mm.⁽³⁾

Sources:

2. Culler, S et al. “Trends in coronary revascularization procedures among Medicare beneficiaries between 2008 and 2012.” *Circulation*, 2015. Vol 131, Issue 4. pp. 362-370.
3. Schunkert, H. et al. “Implications of Small Reference Vessel Diameter in Patients Undergoing Percutaneous Coronary Revascularization.” *Journal of the American College of Cardiology*, 1999; 34:40-8.
